## 13.0. RETENTION

Retention of participants is an essential component of conducting clinical trials so that the investigators can detect differences in outcomes between the intervention and control groups, and so that they can generalize study findings. Sites will use the following strategies to maximize participant retention, including contacting participants at regular intervals between the baseline and 12-month visit to thank them for participating and remind them of their commitment to complete the 12-month visit. At least one of the contacts must be by telephone four-to-eight months after randomization:

**Table 1. Retention strategies by timepoint**  
(apply to ALL participants, regardless of randomized group)

Strategy		Baseline	Between visit	12-month visit
Participant Experience	Careful staff selection & standardized training in rapport building, interviewing techniques, trial-specific protocols, and problem-solving techniques as appropriate to study roles	x	x	x
	Maintain atmosphere that allows participants to feel comfortable and valued, and is professional and efficient	x	x	x
	Contacts by same staff member for continuity as possible while maintaining blinding	x	x	x
	Careful eligibility screening	x		
	Consider clinical no-show rate when determining eligibility*	x		
	Careful explanation of study requirements and random assignment, including importance of attending follow-up visit (even if not adhering to treatment assignment); assurance ppt fully understands expectations	x	x	
	Give clear instructions for completing questionnaires and measurements	x		x
	Keep visits running on time 
 
modified shortened visit to obtain primary outcome data as necessary
 
	x		x
	Snacks or meal vouchers as appropriate*	x		x
	Schedule follow-up at baseline	x		
	Flexible scheduling to accommodate participant's needs	x		x
	Participant incentives, as appropriate, e.g.: 
 
Free parking and/or transportation*
 
Sufficient remuneration
 
	x		x
Participant Engagement	Promote study identity, e.g.: 
 
refrigerator magnet
 
water bottle
 
	x	x	
	Maintain current contact information, including a secondary contact as appropriate	x	x	x
	Maintain regular contact (at least every 4 months), e.g.: 
 
at least one contact by phone four-to-eight months after randomization
 
holiday or birthday cards/calls
 
regular participation reminder letter/calls
 
greet at clinic visits
 
		x	x
	Begin process of scheduling follow-up visit 2-3 months prior to 12-month date			x
	Confirmation letter at least 1 week before appointment			x
	Appointment confirmation call ~3 days before visit			x
	Coordinate study visit with clinic visit to reduce trips	x		x
	Mechanism for monitoring visit cancellations and timely re-scheduling	x	x	x
Ongoing monitoring of recruitment and retention	x	x	x	
Diligent efforts to re-engage inactive participants 
 
multiple methods of contact (phone, text, email, letters)
 
	x	x	x	

We use systematic quality control, adherence to high quality practices, and regular reporting to clinical centers to maintain subject participation in this trial. Examples of training that facilitate retention include thorough and fully informed roles and responsibilities of staff and participants, conveying an appreciation of participation and study identification, nominal remuneration for study visits and parking, and reasonable accommodations to participant schedules. As part of our monthly clinic site calls, we will review retention rates, making comparisons between sites, and re-reviewing high quality practices. We will also work individually with sites that have high participant attrition.

## 14.0. ANALYSIS

### 14.1. Sample size

The primary endpoint is 6MWT distance at 12 months, a continuous scale outcome. An overall sample size of 680, with 340 in each treatment group, will allow detection of a standardized mean difference (Cohen's  $d$ ) of 0.28 between the intervention and UC groups with a power of 90%, two-sided  $\alpha = 0.05$ , and assuming at least 80% retention at 12 months. The decision to use a Cohen's  $d$  of 0.28 is based on based on 30m as the MID for 6MWT distance. In the CONCERT study, the Cohen's  $d$  effect size was approximately 0.39 for 6MWT distance between the overweight and obese groups. A two-sample t-test is used to estimate power (**Table 11**). No multiplicity adjustment will be made for secondary analyses, which are intended to complement the primary findings and to inform future research. They will be interpreted within that context, considering the totality of evidence available.

**Table 11 Continuous Outcome: 6MWT distance**

6MW (m)	Cohen's $d$	$\alpha$	$\beta$	$power$	Sample size for each group	Sample size for each group assuming 20% attrition rate
24.8	.23	.05	0.10	0.90	499	399
30.2	.28	.05	0.10	0.90	336	268
35.6	.33	.05	0.10	0.90	242	193

### 14.2. Overview of analysis plan

This is a patient-randomized trial with patients nested within site and repeated measures within patient. This type of design makes it invalid to use standard approaches to assess a patient-level randomized trial because of the correlation between patients within site and repeated measures within patient. For the primary analysis, we will be evaluating the effect of the intervention at the primary endpoint (12 months through modeling of baseline and 12-month outcomes). It is reasonable to expect that patients within a site are not independent of one another and that repeated measures within patient are not independent from one another. These effects, depending on the correlations within and across sites and patients, may lead to decreased variance at the outcome measurement level and increase the probability of a type I error. The primary research hypothesis to be tested is that the intervention will lead to net improvement in 6MWT distance at 12 months. A linear mixed-effects model (LMM) will be necessary to assess the effect of the treatment. The statistical test will be two-sided because it is possible that the control group is superior to the intervention in either outcome measure. In other words, the statistical alternative hypothesis is two-sided, namely, the two study groups will result in significantly different 6MWT distances at 12 months.

Statistical analysis will occur in two phases. First, preliminary analyses will be performed to examine the suitability and feasibility of assumptions required to conduct more complex analysis including distributional assumptions (e.g., variance homogeneity, normality, etc.), collinearity and independence will be carried out. Second, we will conduct hypothesis testing analyses for the specific aims as described below.

### 14.3. Baseline Analysis and Descriptive Statistics

Equivalence of participants in the intervention and control arms will be assessed on demographic and clinical variables, including outcomes, health status, co-morbidity, and utilization variables. Because this is a randomized controlled trial, no systematic bias is anticipated. However, we will conduct sensitivity analyses that adjust for the covariates that are thought a priori to be related to the primary and secondary outcomes (e.g., age, sex). We will report summary statistics for all baseline covariates and outcomes (means, standard deviations, and quartiles for continuous variables; frequencies and percentages for binary variables) by randomized treatment group.

### 14.4. Drop Outs and Missing Data

We will make every effort to obtain complete data on each study participant at all data collection points. However, some missing data is inevitable and creates a risk for selection bias that can skew results. We will document and evaluate the extent, pattern, and reasons for missing data. Our primary analysis model will

handle missing data using restricted maximum likelihood (REML) estimation which relies on the assumption that the data is missing at random (MAR). ML has been shown to yield similar results to its alternative multiple imputation (MI). ML is a powerful alternative to MI and valid for our data as we will collect all patient demographics prior to randomization. This means that we expect to have no missing values in our explanatory variables, which is a necessary criterion for REML. For the MAR assumption to hold, it must be believed that the probability the outcome is missing depends only on the information available. In the case of this study, this assumption should be acceptable as the missing outcome variables should be explained by the available variables. However, should the MAR assumption appear to be violated, we will conduct sensitivity analyses that instead assume the data are missing not at random. In this case, it is necessary to account for the missing data mechanism in the model.

#### 14.5. Primary Analysis for Aim 1

The primary analysis will use intention-to-treat and all available data in model fitting. Our continuous primary outcomes and important secondary outcomes – 6MWT distance (primary), weight (secondary), and post-walk modified Borg dyspnea scale (secondary) – will be modeled via mixed-effects linear regression of the following form:

$$y_{ijk} = \beta_0 + \beta_1 k + \beta_2 (\text{Intervention}_i * k) + \beta_3 \text{COVID}_{ik} + \beta_4 \text{BaselineSmoker}_i + \alpha_i + \gamma_j + e_{ijk}$$

Where  $y_{ijk}$  stands for the outcome measurement for patient  $i$  of site  $j$  at time point  $k$  ( $k$  is equal to 0 at baseline and is equal to 1 at 12-month follow-up).  $\text{Intervention}_i$  is an indicator variable equal to 1 for patients randomized to the intervention arm and is equal to 0 otherwise.  $\text{COVID}_{ik}$  is an indicator equal to 1 if  $y_{ijk}$  was measured on or after March 19, 2020 and is equal to 0 otherwise.  $\text{BaselineSmoker}_i$  is equal to 1 if patient  $i$  reported smoking within one month prior to baseline self-report and is equal to 0 otherwise. The  $\alpha_i$  are random patient-level intercepts assumed independently distributed  $\text{Normal}(0, \sigma_\alpha^2)$ , the  $\gamma_j$  are random site-level intercepts assumed independently distributed  $\text{Normal}(0, \sigma_\gamma^2)$ , and the  $e_{ijk}$  are outcome-level errors assumed independently distributed  $\text{Normal}(0, \sigma^2)$ .

To compare the intervention arm to the control arm at significance level  $\alpha = 0.05$  with respect to each outcome, an adjusted difference in means estimate, 95% confidence interval, and p-value for testing whether the adjusted difference in means at 12-month follow-up is unequal to zero will be generated based on each primary analysis model's  $\beta_2$  parameter.

We will verify that the linear mixed effects model-based results are not sensitive to violations of model assumptions with permutation and bootstrap resampling tests.

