#### 14.6. Sensitivity Analyses

We will summarize and visualize our outcomes based on missingness patterns across time. If this investigation produces evidences of missingness not at random, a multiple imputation using chained equations (MICE) approach will be implemented as a sensitivity analysis for each primary analysis model, with Rubin's rules employed to pool inference across analyses of completed datasets.

We will also investigate whether the distribution of follow-up measurement time differs across treatment arm. If a difference is evidenced, each primary analysis model and MICE sensitivity analysis model, if using, will be re-fit with a continuous covariate that counts the number of days from 12-months post-randomization date to actual follow-up measurement date.

Additional covariates (e.g., age, sex) will be included to elucidate the primary intention-to-treat findings regarding treatment arm difference in our outcomes at 12-month follow-up. Further sensitivity analyses will be conducted using Generalized Estimating Equations (GEEs) if the distributional assumption of normality is not met within the LMM framework. GEEs do not rely on this distributional assumption and will allow for an evaluation of the intervention in this scenario.

#### 14.7. Secondary Analysis for Aim 1

Dichotomized secondary outcomes for 6MWT distance, weight, and post-walk modified Borg dyspnea scale will be generated based on whether the respective, continuously measured primary outcome meets or exceeds the minimal important difference, as described below:

- 6MWT distance: 30m
  - Dichotomous outcome is equal to 1 if (follow-up 6MWT distance - baseline 6MWT distance)  $\geq$  30m, and it is equal to 0 otherwise.
- Weight: (Multiple)
  - Dichotomous outcome is equal to 1 if (follow-up weight – baseline weight)/(baseline weight)\*100%  $\geq$  5%, and it is equal to 0 otherwise.
  - Dichotomous outcome is equal to 1 if (follow-up weight – baseline weight)/(baseline weight)\*100%  $\geq$  3%, and it is equal to 0 otherwise.
- Post-walk modified Borg dyspnea scale (i.e., shortness of breath): 1 unit
  - Dichotomous outcome is equal to 1 if (baseline shortness of breath - follow-up shortness of breath)  $\geq$  1 unit, and it is equal to 0 otherwise.

Mixed-effects logistic regression models of the following form will be fit to these secondary outcomes and used to estimate a treatment arm standardized risk difference:

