$$y_{ij} = \beta_0 + \beta_1 \text{Intervention}_i + \beta_2 \text{COVID}_i + \beta_3 \text{BaselineSmoker}_i + \gamma_j + e_{ij}$$

Where  $y_{ij}$  stands for the dichotomized outcome for patient  $i$  of site  $j$ .  $\text{Intervention}_i$  is an indicator variable equal to 1 for patients randomized to the intervention arm and is equal to 0 otherwise.  $\text{COVID}_i$  is an indicator equal to 1 for patients whose follow-up outcome was measured on or after March 19, 2020 and is equal to 0 otherwise.  $\text{BaselineSmoker}_i$  is equal to 1 if patient  $i$  reported smoking within one month prior to baseline self-report and is equal to 0 otherwise. The  $\gamma_j$  are random site-level intercepts assumed independently distributed Normal(0,  $\sigma_\gamma^2$ ), and the  $e_{ijk}$  are outcome-level errors assumed independently distributed Normal(0,  $\sigma^2$ ).

Additional secondary outcomes – generic HRQoL, Framingham CVD Risk Score, waist circumference, blood pressure, and BMI – will be analyzed similarly as in the primary and secondary analyses of 6MWT distance, weight, and post-walk modified Borg dyspnea scale.

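### The primary model forces equal 6MWT variance at baseline and 12 months; an unstructured 2×2 covariance protects the error rate and the interval at no cost

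*Combined protocol and SAP*

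**What the plan says.** Section 14.5 models both visits together with a common baseline mean. The patient effects "are random patient-level intercepts assumed independently distributed" normal with a single variance. The site effects have another single variance, and the residuals "are outcome-level errors assumed independently distributed" normal with one variance that serves both visits. The estimate, 95% confidence interval and p-value for 12 months "will be generated based on each primary analysis model's" β2 parameter.

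Three other provisions bear on this:

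- Section 14.2 lists variance homogeneity among the assumptions to be examined before hypothesis testing. It does not say what follows if the check fails.
- Section 14.5 ends: "We will verify that the linear mixed effects model-based results are not sensitive to violations of model assumptions", by permutation and bootstrap tests. It does not say which result prevails if they disagree.
- Section 14.6 adds GEE, but only "if the distributional assumption of normality is not met within the LMM framework".

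Weight and post-walk Borg dyspnea use the same model (14.5). Further secondary outcomes "will be analyzed similarly as in the primary and secondary analyses of 6MWT distance, weight, and post-walk modified Borg dyspnea scale" (14.7).

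**The concern.** With one patient, one site and one residual variance, the model variance of 6MWT distance is the same sum at baseline and at 12 months. Nothing in the documents supports that equality. Let r be the 12-month SD divided by the baseline SD. The fitted common variance settles between the two true values, whereas the error in β2 is driven mainly by the 12-month spread. So r > 1 gives an interval that is too narrow and more than 5% false positives. r < 1 gives a conservative test and an interval wider than necessary. This affects the trial's only confirmatory test.

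**Working it through.** **Inputs from the documents.** 340 per arm, two-sided α = 0.05 and 80% retention (14.1), so 340 × 0.8 = 272 completers per arm. Table 11 implies an SD of 30.2/0.28 = 107.9, about 108 m. As a check on these inputs, 2(1.960 + 1.282)²/0.28² = 268 evaluable per arm, and 268/0.8 = 335. Table 11 has 268 and 336, so it reproduces to rounding.

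**Assumed, not in the documents.** r; the correlation ρ between visits (0.60 to 0.85); loss completely at random; 108 m taken as the baseline SD.

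**Formulas.** With a common baseline mean, β2 is estimated by the between-arm difference in completers' mean of y1 − q·y0, where q is the fitted correlation and v the fitted common variance. In units of the baseline variance:

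- model variance ∝ v(1 − q²)
- true variance ∝ r² − 2qρr + q²
- R = true/model; type I error = 2[1 − Φ(1.96/√R)]

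Each variance is multiplied by 108² × 2/272.

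**Complete data.** Here v = m = (1 + r²)/2 and q = ρr/m. Because 2m − 1 = r², R reduces to 2r²/(1 + r²), and ρ cancels. At r = 0.90, 1.10 and 1.20, R = 1.62/1.81 = 0.895, 2.42/2.21 = 1.095 and 2.88/2.44 = 1.180. Type I error is 3.8%, 6.1% and 7.1%.

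**With 20% missing.** v and q minimise 0.8[log|V| + tr(V⁻¹S)] + 0.2[log v + 1/v], with S the true covariance and V the equal-variance one. Example, r = 1.10 and ρ = 0.75: v = 1.0879, q = 0.7433.

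- Model: 1.0879 × (1 − 0.5525) = 0.4868, so SE = 108√(0.4868 × 2/272) = 6.46 m.
- True: 1.21 − 2(0.7433)(0.825) + 0.5525 = 0.5361, so SE = 6.78 m.
- R = 1.101; 1.96/√1.101 = 1.868; type I error 6.2%.
- Unstructured: r²(1 − ρ²) = 1.21 × 0.4375 = 0.5294, so SE = 6.74 m.

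| r | R at ρ = 0.60 / 0.75 / 0.85 | Type I error | CI coverage | 95% half-width, ρ = 0.75: as written / unstructured | Simulated type I error, ρ = 0.75: as written / unstructured |
|---|---|---|---|---|---|
| 0.90 | 0.890 / 0.892 / 0.894 | 3.8% | 96.2% | 11.5 / 10.8 m | 3.7% / 4.9% |
| 1.00 | 1 / 1 / 1 | 5.0% | 95.0% | 12.0 / 12.0 m | 5.2% / 5.1% |
| 1.10 | 1.103 / 1.101 / 1.100 | 6.2% | 93.8% | 12.7 / 13.2 m | 6.3% / 5.1% |
| 1.20 | 1.198 / 1.195 / 1.192 | 7.3% | 92.7% | 13.5 / 14.4 m | 7.3% / 5.1% |

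At r = 0.95 and 1.05 the type I error is 4.4% and 5.6%. The simulation used 16,000 trials per cell (Monte Carlo SE about 0.2 points) and left out the site, smoking and COVID terms. An analytic calculation with those terms (ρ = 0.7, assuming 20 sites, site variance 5% of baseline variance, 30% smokers and 30% of 12-month visits after the COVID date) gives 3.8%, 5.0%, 6.2% and 7.3%.

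**When the verdict would change.** A true p of 0.05 appears as a model p of 2[1 − Φ(1.96√R)]. Model p of about 0.040–0.050 at r = 1.10, or 0.032–0.050 at r = 1.20, would not be significant with a correct SE. Model p of 0.050–0.064 at r = 0.90 would be.

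**Power for 30 m (ρ = 0.75), as written / unstructured.** 99.97% / 99.99% at r = 0.90; 98.5% / 98.3% at r = 1.20.

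**The case against.** The strongest reply is that no defect in this trial is shown. The documents give no reason to expect the SD to move by 10% or 20%, and at 5% the error is only 4.4% or 5.6%. That is right, and it is why this is put as a conditional improvement.

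Second, the plan already checks variance homogeneity and commits unconditionally to resampling. A permutation test on the same estimate does hold its size: 4.9% at r = 0.90 and 4.7% at r = 1.20 in 1,500 simulated trials. This lowers the seriousness. But the plan is silent on what follows a failed check or a disagreement, and the β2 interval and p-value remain the stated primary result. Choosing the remedy after seeing the disagreement is what a pre-specified plan should avoid.

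Third, the size depends on how the spread changes. If only the intervention arm's SD changes, type I error is 5.6% at r = 1.10 and 6.2% at r = 1.20 (ρ = 0.75, 20% missing), roughly half the excess.

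Fourth, 108 m could equally be the 12-month SD, since the endpoint is distance at 12 months. The half-widths at ρ = 0.75 would then be 12.8 against 12.0 m, 11.5 against 12.0 m and 11.2 against 12.0 m at r = 0.90, 1.10 and 1.20. The error rates do not change.

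Finally, the p-value bands correct the SE of the existing estimate. The unstructured fit also shifts the point estimate slightly, so the bands are a guide and not an exact rule.

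**Conclusion.** The point holds. Equal variance at the two visits is imposed on the primary test without support, and the standard error is wrong in either direction if it fails. For a 10% to 20% change in SD common to both arms, the departure from 5% is between 1 and 2.5 percentage points (3.8%, 6.2%, 7.3%), and the result hardly depends on ρ. It rests on an assumed r whose direction is unknown, and on loss completely at random. The practical reach is limited: detection of a true 30 m effect is not threatened, and significance changes only near the threshold, although interval coverage is off at any p-value. No error size is claimed for the secondary outcomes, since no SD ratio is available for them. The change should be made because the exposure is avoidable at almost no cost.

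**What to change.** Keep the fixed effects, common baseline mean, site random intercept and REML. Replace the patient random intercept plus common residual with an unstructured 2×2 within-patient covariance: separate variances at baseline and 12 months and a free covariance. Apply it to 6MWT distance and to the other continuous outcomes that use this model. State that β2 from this fit, with its interval and p-value, is the primary result, and that the permutation and bootstrap results are supportive.

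The cost is one covariance option in the code, one sentence in section 14.5, and one extra variance parameter with about 680 participants. At equal SDs (ρ = 0.75) the analytic SE is 6.13 m under both structures, and the simulated mean SEs are 6.12 and 6.13 m.

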#### 14.6. Sensitivity Analyses

We will summarize and visualize our outcomes based on missingness patterns across time. If this investigation produces evidences of missingness not at random, a multiple imputation using chained equations (MICE) approach will be implemented as a sensitivity analysis for each primary analysis model, with Rubin's rules employed to pool inference across analyses of completed datasets.

We will also investigate whether the distribution of follow-up measurement time differs across treatment arm. If a difference is evidenced, each primary analysis model and MICE sensitivity analysis model, if using, will be re-fit with a continuous covariate that counts the number of days from 12-months post-randomization date to actual follow-up measurement date.

Additional covariates (e.g., age, sex) will be included to elucidate the primary intention-to-treat findings regarding treatment arm difference in our outcomes at 12-month follow-up. Further sensitivity analyses will be conducted using Generalized Estimating Equations (GEEs) if the distributional assumption of normality is not met within the LMM framework. GEEs do not rely on this distributional assumption and will allow for an evaluation of the intervention in this scenario.

#### 14.7. Secondary Analysis for Aim 1

Dichotomized secondary outcomes for 6MWT distance, weight, and post-walk modified Borg dyspnea scale will be generated based on whether the respective, continuously measured primary outcome meets or exceeds the minimal important difference, as described below:

- 6MWT distance: 30m
  - Dichotomous outcome is equal to 1 if (follow-up 6MWT distance - baseline 6MWT distance)  $\geq$  30m, and it is equal to 0 otherwise.
- Weight: (Multiple)
  - Dichotomous outcome is equal to 1 if (follow-up weight – baseline weight)/(baseline weight)\*100%  $\geq$  5%, and it is equal to 0 otherwise.
  - Dichotomous outcome is equal to 1 if (follow-up weight – baseline weight)/(baseline weight)\*100%  $\geq$  3%, and it is equal to 0 otherwise.
- Post-walk modified Borg dyspnea scale (i.e., shortness of breath): 1 unit
  - Dichotomous outcome is equal to 1 if (baseline shortness of breath - follow-up shortness of breath)  $\geq$  1 unit, and it is equal to 0 otherwise.

Mixed-effects logistic regression models of the following form will be fit to these secondary outcomes and used to estimate a treatment arm standardized risk difference:

$$y_{ij} = \beta_0 + \beta_1 \text{Intervention}_i + \beta_2 \text{COVID}_i + \beta_3 \text{BaselineSmoker}_i + \gamma_j + e_{ij}$$

Where  $y_{ij}$  stands for the dichotomized outcome for patient  $i$  of site  $j$ .  $\text{Intervention}_i$  is an indicator variable equal to 1 for patients randomized to the intervention arm and is equal to 0 otherwise.  $\text{COVID}_i$  is an indicator equal to 1 for patients whose follow-up outcome was measured on or after March 19, 2020 and is equal to 0 otherwise.  $\text{BaselineSmoker}_i$  is equal to 1 if patient  $i$  reported smoking within one month prior to baseline self-report and is equal to 0 otherwise. The  $\gamma_j$  are random site-level intercepts assumed independently distributed Normal(0,  $\sigma_\gamma^2$ ), and the  $e_{ijk}$  are outcome-level errors assumed independently distributed Normal(0,  $\sigma^2$ ).

Additional secondary outcomes – generic HRQoL, Framingham CVD Risk Score, waist circumference, blood pressure, and BMI – will be analyzed similarly as in the primary and secondary analyses of 6MWT distance, weight, and post-walk modified Borg dyspnea scale.

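### Section 14.4 commits to an analysis under missing not at random, but the only method Section 14.6 gives for that case, MICE with no stated sensitivity parameter, assumes missing at random

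*Combined protocol and SAP*

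**What the plan says.** Section 14.4 bases the primary mixed model on REML under MAR. It adds a conditional commitment: "However, should the MAR assumption appear to be violated, we will conduct sensitivity analyses that instead assume the data are missing not at random". The next sentence states what such an analysis needs: "In this case, it is necessary to account for the missing data mechanism in the model". The same section promises "We will document and evaluate the extent, pattern, and reasons for missing data" and remarks that maximum likelihood and multiple imputation tend to give similar answers.

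Section 14.6 plans to summarise and plot outcomes by missingness pattern, and then says: "If this investigation produces evidences of missingness not at random, a multiple imputation using chained equations (MICE) approach will be implemented". Results are to be pooled with Rubin's rules. No imputation variables are listed. Sections 14.4 to 14.7 contain no shift parameter, reference-based rule, pattern-mixture model, selection model or tipping point.

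The other planned checks are resampling (Section 14.5: "We will verify that the linear mixed effects model-based results are not sensitive to violations of model assumptions with permutation and bootstrap resampling tests") and, in Section 14.6, a refit with a visit-timing covariate, refits with added covariates, and GEE if normality fails.

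**The concern.** Sections 14.4 and 14.6 respond to the same trigger with different kinds of analysis. Standard MICE draws each missing value from a model fitted to the observed values, so it takes unseen walks to behave like seen walks given the variables in the model. The primary REML fit makes the same kind of assumption. Running one after the other cannot show how far the result depends on it.

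The trigger is also weak. All baseline measures must be complete before randomization (Section 10.3) and the only follow-up is at 12 months (Table 10). For the primary outcome, the missingness pattern is therefore just whether the 12-month walk was seen. Baseline differences between those seen and not seen are fully compatible with MAR. Observed data cannot separate MAR from MNAR here. Recorded reasons for loss can inform a plausible range, but they are not an analysis.

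What is at stake is interpretation. If the trigger fires, close agreement between MICE and REML could be reported as robustness to MNAR that was never tested.

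**Working it through.** **Inputs from the plan.** Section 14.1: "An overall sample size of 680, with 340 in each treatment group", "assuming at least 80% retention at 12 months", d = 0.28, 90% power, two-sided alpha 0.05. Table 11 pairs d = 0.28 with 30.2 m, so SD = 30.2/0.28 = 107.9 m.

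**Reproducing the plan's figure.** Evaluable n per arm = 2(1.96 + 1.2816)²/0.28² = 268.05, rounded up to 269 (Table 11: 268). Dividing by 0.80 gives 337 enrolled (Table 11: 336; planned 340). At 0.80 × 340 = 272 evaluable per arm, power is 0.904. The sample size reproduces, with 268 read as evaluable and 336 as enrolled; the column labels in Table 11 appear to be swapped.

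**Assumptions not in the documents.** The size of the MNAR shift, the correlation rho between baseline and 12-month walk, the observed effect, and the split of loss between arms.

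**Bias formula.** Let p be the missing fraction in an arm and delta the mean departure of its unseen walks from their MAR prediction. Then

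true effect = MAR effect + p(int) × delta(int) − p(ctl) × delta(ctl).

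Starting from 30.2 m:

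- 20% missing per arm, intervention-only shift of −30, −50 or −100 m: 30.2 − 6 = 24.2 m, 30.2 − 10 = 20.2 m, 30.2 − 20 = 10.2 m.
- 20% missing per arm, control-only shift of −50 m: 30.2 + 10 = 40.2 m.
- Equal shifts with equal loss: no change.
- −50 m in both arms with 25% intervention and 15% control loss: 30.2 − 12.5 + 7.5 = 25.2 m; with the losses reversed, 35.2 m.

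**Simulation.** 340 per arm, 20% missing, rho = 0.7, 600 trials per scenario, 20 imputations with Rubin's rules. The MAR likelihood estimate was a baseline-adjusted regression on observed outcomes. Mean estimates in metres:

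| Shift, intervention / control | True | MAR likelihood | Plain MI | Delta-adjusted MI |
|---|---|---|---|---|
| 0 / 0 | 30.2 | 30.0 | 30.0 | 30.1 |
| −30 / 0 | 24.2 | 30.0 | 30.1 | 24.0 |
| −50 / 0 | 20.2 | 29.8 | 29.8 | 19.9 |
| −100 / 0 | 10.2 | 30.5 | 30.5 | 10.6 |
| −30 / −30 | 30.2 | 30.0 | 29.9 | 29.9 |

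Plain MI stayed within about 0.1 m of the likelihood estimate on average. Only the version with a stated delta followed the true effect.

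**Effect on significance.** With the SE held at its MAR value, SE = 107.9 × sqrt((1 − rho²) × 2/272), and significance is lost at an intervention-arm shortfall of (observed effect − 1.96 × SE)/0.2:

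| rho | SE (m) | Tipping shortfall, 30.2 m observed | Tipping shortfall, 20 m observed |
|---|---|---|---|
| 0 | 9.25 | about 60 m | about 9 m |
| 0.5 | 8.01 | about 72.5 m | about 21.5 m |
| 0.75 | 6.12 | about 91 m | about 40 m |
| 0.8 | 5.55 | about 97 m | about 46 m |

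The formula runs slightly high because shifting the imputed values also widens the pooled SE. Simulation with Rubin-pooled SEs at 30.2 m gave about 60, 71, 87 and 94 m. A smaller run (150 trials, true effect 30 m) gave about 56, 68, 87 and 90 m.

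**The case against.** **MICE can be made MNAR.** It is an algorithm that can carry a shift, and Section 14.4 does say the mechanism must enter the model, so this might be thin specification rather than a mislabelled method. But no MNAR parameter is stated anywhere, and an analyst following Section 14.6 literally would run a MAR imputation.

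**MICE may still help.** With auxiliary variables it can differ from REML. In one simulated case, an auxiliary correlated 0.5 with the residual drove intervention-arm loss on top of a −50 m shift. REML gave 37.5 m, MICE with the auxiliary 30.6 m, and the true effect was 20.2 m. MICE removed 6.9 of 17.3 m of bias, about 40%. That stands, but it tests a wider MAR condition. The 10.4 m left is essentially the MNAR part (0.2 × 50 = 10 m). The verdict does not depend on this single scenario.

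**Other checks do vary the assumption.** Ordinary GEE generally needs a stricter missingness assumption than REML, and added covariates change what MAR is conditional on. Both are true, but neither moves towards MNAR, and GEE is planned only for non-normality. The accurate statement is that no other specified check assumes MNAR.

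**The sizes are hypothetical.** Loss of 20% is a planning ceiling, Section 13 sets out substantial retention work in both arms, and loss from COVID-19 visit suspensions (Section 10.5) could be similar between arms. At the planned effect the tipping shortfall is two to three times the 30 m minimal important difference, in one arm only. All of this stands. It limits how alarming the point is, but it does not make the fallback an MNAR analysis.

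**Conclusion.** The concern holds. Sections 14.4 and 14.6 contradict each other on what will be done if MAR is doubted, and the method specified cannot deliver what Section 14.4 commits to. The missed bias is 0.2 times the between-arm difference in shift when 20% is missing in each arm: 6, 10 or 20 m for one-arm shifts of 30, 50 or 100 m. A significant result at the planned 30.2 m would be fairly robust, while one at an observed 20 m could be overturned by a shortfall of roughly 9 to 46 m, depending on rho. Without a tipping point, readers cannot tell which case applies. These sizes rest on assumed shifts, correlations and loss; the contradiction does not. The primary estimate and test are unchanged, so this should be fixed but does not invalidate the primary analysis.

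**What to change.** 1. Reconcile Sections 14.4 and 14.6, and remove the dependence on finding evidence of MNAR in the observed data.
2. Prespecify a delta-adjusted (pattern-mixture) multiple imputation of 12-month 6MWT distance: impute under MAR, shift the imputed values over a fixed grid varied separately by arm, pool with Rubin's rules, and report the tipping point. Other MNAR methods would serve if fully specified. Justify the grid range from recorded reasons for missingness.
3. Keep plain MICE, call it a MAR analysis, and list its auxiliary variables. Baseline FEV1, SGRQ-C, Borg score, age, sex and health care utilization are already collected.
4. As a side item, state how deaths before 12 months are handled, as an estimand choice separate from missing data.

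The cost is SAP wording and some extra programming. No new data are needed.
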